10.5. Vital Signs

Vital sign measurements including sitting systolic blood pressure, sitting diastolic blood pressure, sitting pulse rate, supine orthostatic systolic blood pressure, supine orthostatic diastolic blood pressure, supine pulse rate, standing orthostatic systolic blood pressure, standing orthostatic blood pressure, and standing pulse rate at each scheduled time and changes from baseline in vital sign measurements will be summarized with descriptive statistics at each scheduled time point by treatment group.

Body height will be measured at Screening only and will be summarized by treatment group. Weight will be measured at each schedule visit and, along with changes from baseline, will be summarized with descriptive statistics at each scheduled time point by treatment group. Weight gain \geq 7% of body weight will be tabulated. Weight will be displayed in kilograms; height will be displayed in centimeters.

Body mass index (BMI) will be derived from the weight at each visit and from height (at screening), along with changes from baseline, will be summarized with descriptive statistics at each schedule timepoint by treatment group. BMI will be displayed in kilograms per meter squared.

All vital signs data will be presented in a listing.

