Five open-label safety, tolerability and Phase 2 studies of ecopipam in 56 subjects with schizophrenia were conducted. Subjects diagnosed with acute schizophrenia, schizophreniform disorder, or bipolar schizoaffective disorders were treated with ecopipam HCl up to a daily dose of 600 mg. The maximum duration of treatment was six weeks. Ecopipam, when administered to subjects with schizophrenia, did not demonstrate efficacy in these studies. The most commonly reported adverse events were somnolence (21%, 12/56), headache, nausea, vomiting and dizziness (each reported in 14%, 8/56 subjects), insomnia (9%, 5/56), dyspepsia (7%, 4/56), and anxiety (7%, 4/56).

In a Phase 2, double-blind, placebo-controlled study (C/I98-271), 185 subjects with a primary diagnosis of moderate to severe obesity were treated with ecopipam HCl (10, 30, or 100 mg PO, once per day) for 12 weeks. Subjects receiving ecopipam HCl showed a dose-dependent weight loss. The most commonly reported adverse events by subjects receiving ecopipam HCl were headache, 19% (36/185), viral infection, 19% (36/185), somnolence, 18% (34/185), insomnia, 9% (17/185), and nausea, 9% (16/185).

In three Phase 3, double-blind, placebo-controlled studies (P00359, P00396, and P00741), obese subjects including type 2 diabetic subjects were treated with ecopipam HCl (50 or 100 mg PO, QD) for 52 weeks. Subjects receiving ecopipam HCl showed a dose-dependent weight loss. These Phase 3 studies were discontinued because of unexpected psychiatric adverse events (ecopipam 31% vs. placebo 15%), including depression, anxiety, and suicidal ideation, thereby excluding its projected use in weight management. The most frequently reported adverse events in all Phase 3 obesity studies receiving ecopipam HCl were upper respiratory tract infection, 30% (439 of 1482 subjects reporting), insomnia 17% (248/1482), headache, 16% (244/1482), depression, 16% (236/1482), somnolence, 15% (216/1482), fatigue, 15% (215/1482), anxiety, 14% (211/1482), pharyngitis, 9% (137/1482), back pain, 8% (114/1482), nausea, 7% (107/1482). The frequencies of insomnia, depression, somnolence and anxiety were about twice as frequent in subjects receiving ecopipam HCl compared to placebo. The frequencies of upper respiratory

tract infection, headache, fatigue, pharyngitis, back pain and nausea were similar in frequencies in subjects receiving ecopipam and placebo.

Clinical Summary: Legacy Psyadon Studies in Indications other than TS

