In subjects with TS, ecopipam has been evaluated in two studies, one study in adult subjects with TS and one study in children/adolescents with TS. In the pediatric TS study, overall, adverse events were more common in ecopipam compared to placebo. There were no serious adverse events (SAEs) and only one subject discontinued treatment due to an adverse event in the ecopipam group. Most adverse events were mild to moderate in severity. Adverse events in the Psychiatric Disorders, Central Nervous System Disorders and Gastrointestinal Disorders categories were more common with ecopipam than placebo. Notably, more subjects experienced adverse events of somnolence, insomnia, sedation, restlessness, irritability, nausea and vomiting with ecopipam than with placebo. There were no AEs of extra-pyramidal symptoms in the pediatric study. A higher percentage of subjects on ecopipam gained 5 pounds or more during the study than with placebo (17.5% compared to 15%). Orthostatic blood pressure assessments were not done (or not reported). A table of weight changes was provided for the open-label extension study (PSY302A) and almost all of the children gained weight after 3, 6, 9 or 12 months of treatment. Suicidal ideation was seen both during the blinded study as well as the open-label extension study in pediatric subjects ecopipam. There did not appear to be clinically significant ECG findings. However, open-label extension adverse event data have not yet been analyzed.

In the adult study in TS, the most commonly reported adverse events (incidence $\geq 20\%$) were sedation (33%), insomnia (33%), fatigue (33%), somnolence (28%), headache (22%), muscle twitching (22%) and anxiety (22%). Two subjects developed adverse event of akathisia and one developed an adverse event of tremor, both of which are extrapyramidal reactions. Three of 18 subjects (16.7%) also discontinued study drug due to an adverse event.

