5.3.2. Assessment of Benefit

A review of the efficacy evaluations for ecopipam in the two studies conducted in subjects with TS reveals improvement on the YGTSS scores and other measures of illness severity from baseline to end point.

In a Phase 2a, open-label, non-randomized study (PSY301), the activity and safety of ecopipam in 18 adult subjects with TS was evaluated. Subjects were to receive ecopipam HCl 50 mg for 2 weeks followed by 100 mg for 6 weeks. The primary outcome measure was the YGTSS Total (MP) score. After ecopipam treatment, the YGTSS Total score, motor tics score, phonic tics score and overall impairment decreased from baseline to endpoint, suggesting that the severity of tics was decreased (Table 16, Investigator's Brochure).

In a Phase 2b double-blind, randomized crossover study in children/adolescents (ages 7-17 years) with TS (PSY302), 40 subjects were enrolled and 38 (95.0%) completed the study. The primary endpoint was the YGTSS Total (MP) score.

Ecopipam treatment resulted in a numerical decrease in the YGTSS Total score relative to the placebo treatment, but the decrease was not statistically significant (Figure 9, Investigator's Brochure). The least squares means (\pm SE) of the difference between ecopipam and placebo treatment were -2.8885 (\pm 1.5282); 95% CI: -5.9822, 0.2053, p=0.0664) on Day 16 and -2.1366 (\pm 1.6551; 95% CI: -5.4871, 1.2139, p=0.2045) on Day 30.

Based on the available safety data, there are some safety advantages for ecopipam compared to D2 antagonists, but the full measure of differentiation will not be known until after a larger and longer Phase 3 program. The rate of tardive dyskinesia and other extrapyramidal reactions commonly associated with D2 antagonists appears much lower with ecopipam. Other possible advantages include a decreased risk of lipid changes, hyperglycemia and orthostatic hypotension.

An individual subject may not receive any therapeutic benefit from participating in an investigational study however, by contributing to medical research, others will be helped. All subjects participating in the study will receive physical examinations, various laboratory tests, ECGs and a systematic evaluation of their condition. Ecopipam may help improve symptoms for participants.

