6.1. General Methods

All analyses and outputs will be produced using SAS[®] version 9.4 or later. Unless otherwise specified, efficacy and safety summaries will be presented for each treatment. All other summaries will be presented for each treatment and overall. Continuous variables will be summarized using the number of observations (n), mean, standard deviation (SD), median, minimum, and maximum. Categorical variables will be summarized using number of observations (n), frequency, and percentages of subjects.

All relevant subject data will be included in listings. All randomized subjects entered into the database will be included in subject data listings. All by visit summaries will use the nominal visit. Unscheduled visits will not be summarized but will be included in the listings.

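### SAP 10.5 derives no standing-minus-supine change and tabulates weight gain only, so measured orthostatic falls and measured weight loss are counted by arm only if reported as adverse events

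*SAP*

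**What the plan says.** **Collection.** The Protocol schedule of assessments (footnote b) and Protocol 12.1.3 require blood pressure after 5 minutes supine and again after 3 minutes standing. This is done at Screening, Baseline, Weeks 4, 6, 8 and 12, and the 7- and 14-day follow-up visits. Weight is taken at the same visits.

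**Planned blood pressure tables.** SAP 10.5 lists the positions one by one: "supine orthostatic systolic blood pressure, supine orthostatic diastolic blood pressure, supine pulse rate, standing orthostatic systolic blood pressure". From that last item the list runs on as "standing orthostatic systolic blood pressure, standing orthostatic blood pressure, and standing pulse rate at each scheduled time and changes from baseline". The values and the "changes from baseline in vital sign measurements will be summarized with descriptive statistics at each scheduled time point by treatment group". SAP 6.1 defines the statistics: "Continuous variables will be summarized using the number of observations (n), mean, standard deviation (SD), median, minimum, and maximum". All vital signs are also listed by subject.

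**Planned weight tables.** Weight and its change from baseline get the same descriptive statistics, displayed in kilograms. One categorical table is added: weight gain of at least "7% of body weight will be tabulated". No matching row exists for loss.

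**Background.** On the earlier paediatric Tourette study, Protocol 5.3.1 states: "Orthostatic blood pressure assessments were not done (or not reported". For the older obesity and cocaine programme it reports no raw orthostatic data. On weight in the adult obesity studies, Protocol 5.2.2.1 states: "Subjects receiving ecopipam HCl showed a dose-dependent weight loss".

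**The concern.** An orthostatic fall is a within-subject quantity: the same child's standing reading compared with that child's supine reading a few minutes earlier. The protocol collects the pair, but the SAP separates it before summarising. A marked weight loss is likewise an individual event, and the plan counts individual weight change in one direction only.

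What is at stake is safety detection. If a minority of children on one arm have sizeable measured falls or losses without symptoms, no planned table shows how many there were. Cut-offs chosen after unblinding, once someone asks the question, would be post hoc.

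**Working it through.** The plan states no figure on this point, so the first step is to ask what the planned tables can and cannot recover.

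**1. Average orthostatic change: recoverable.** If the same subjects contribute both positions, mean(standing − supine) = mean(standing) − mean(supine). A reader can subtract the two reported means.

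**2. Number of subjects with a fall: not recoverable.** The spread of the paired difference is

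SD_diff = √(SD_sup² + SD_st² − 2ρ·SD_sup·SD_st),

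which is SD·√(2(1−ρ)) when both SDs are equal. The within-subject correlation ρ appears in no planned table. The minimum and maximum by position do not supply it: the lowest standing reading may belong to a child whose supine reading was also low, and the largest fall may belong to a child whose standing reading is unremarkable.

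**3. Illustration.** Only the 75 per arm comes from the documents. The assumptions are a normal model, a mean supine-to-standing systolic fall of 2 mmHg, equal SDs of 8 to 12 mmHg in each position, and one visit. The 15 mmHg cut-off is arbitrary and not a clinical proposal.

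Expected count per arm = 75 × [1 − Φ((15 − 2)/SD_diff)].

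At SD 10:
- ρ = 0.5: SD_diff = 10.0, z = 1.30, tail 9.7%, count 7.3
- ρ = 0.7: SD_diff = 7.75, z = 1.68, tail 4.7%, count 3.5
- ρ = 0.9: SD_diff = 4.47, z = 2.91, tail 0.2%, count 0.1

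| SD per position | ρ = 0.5 | ρ = 0.7 | ρ = 0.9 |
|---|---|---|---|
| 8 | 3.9 | 1.3 | 0.0 |
| 10 | 7.3 | 3.5 | 0.1 |
| 12 | 10.4 | 6.1 | 0.6 |

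At SD 10, a 10 mmHg cut-off gives 15.9, 11.3 and 2.8, and a 20 mmHg cut-off gives 2.7, 0.8 and 0.0. Within any row of the table, the expected supine and standing means and SDs are the same for every ρ.

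**4. Weight.** The minimum of the change shows the largest loss in kilograms in each arm at each visit. It does not show how many subjects lost weight, or the loss relative to body size. That matters in a trial with weight bands running from 18 kg to above 83 kg: 7% of 18 kg is 0.07 × 18 = 1.26 kg, and 7% of 83 kg is 0.07 × 83 = 5.81 kg.

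Assume a mean weight change of 0 to +3% with SD 3 to 5%. The expected number per arm losing at least 7%, 75 × Φ((−7 − m)/s), runs from 0.03 (m = 3, s = 3) to 6.1 (m = 0, s = 5). None of these would have a categorical row. The corresponding number gaining at least 7%, which is counted, runs from 0.7 (m = 0, s = 3) to 15.9 (m = 3, s = 5).

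**5. The other route to a count.** SAP 10.3 tabulates adverse events by arm and preferred term, and its Parkinsonism list of events of special interest includes decreased weight as a term. But under Protocol 12.2.1, an abnormal vital sign becomes an adverse event only if it produces signs or symptoms, needs intervention, leads to interruption or discontinuation of study drug, or is judged clinically significant. Measured changes below that bar stay in the listing. Orthostatic hypotension is in neither of the SAP's lists of events of special interest.

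**The case against.** The strongest reply is that the plan is not blind to these events. Reported orthostatic hypotension appears in the by-arm adverse event tables. Decreased weight, dizziness, falls and balance disorder are named terms of special interest, counted once per patient. The vital-sign summaries go beyond means, and everything is listed. All of this stands, so a reader who infers that such events are never counted by arm would be wrong. The gap is confined to measured changes not reported as adverse events. For orthostatic pressure, that leaves by-arm counts on the footing Protocol 5.3.1 describes for the older programme: changes not documented, and no adverse events of orthostatic hypotension seen.

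A second reply is that a gain-only weight table has a stated basis. Protocol 5.3.1 reports 17.5% on ecopipam against 15% on placebo gaining 5 pounds or more in the paediatric study, and weight gain in almost all children in its extension. Protocol 12.2.1.3 names weight gain as an event of special interest. The paediatric study summary in Protocol 5.2.2.1 found no evidence of an effect on weight, and the weight loss was seen in adults with obesity. This justifies keeping the gain table. It does not justify omitting loss, which the SAP itself treats as a term of interest.

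Two further inferences are tempting and unsupported. Protocol 5.3.2 says: "Other possible advantages include a decreased risk of lipid changes, hyperglycemia and orthostatic hypotension". A reader might conclude that the missing tables stop the trial from testing that statement. But the comparison there is with D2 antagonists, and this trial has only a placebo comparator, so no table could test it. A reader might also assume that the paired readings were added because earlier orthostatic data were missing. The protocol gives no rationale for them.

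**Conclusion.** The gap is real and narrow. As written, SAP 10.5 yields no by-arm count of subjects with a measured orthostatic fall or a measured weight loss; only those reported as adverse events are counted. The paired data needed for the first count are already collected, in a population for which the protocol reports no earlier orthostatic measurements.

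The documents contain no figure for the size of the gap. The 0 to 10 falls per arm in the 15 mmHg table, and the 0 to 6 weight losses, rest wholly on assumed SDs, correlations, means and cut-offs. They show only that the planned tables do not determine the counts. They say nothing about what ecopipam does. Because safety is summarised descriptively, loss of statistical power is not the argument here.

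The primary analysis and type I error are untouched. This is an inexpensive improvement in safety reporting and worth making before unblinding.

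**What to change.** Add to SAP 10.5:

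1. Standing minus supine systolic pressure, diastolic pressure and pulse, derived per subject and visit and summarised with change from baseline by arm.
2. A by-arm count of subjects with any post-baseline orthostatic fall, at cut-offs the sponsor sets before unblinding. The denominator should be subjects with at least one post-baseline supine/standing pair, since visits may be held remotely, and the text should say whether the off-drug follow-up visits are included.
3. A weight-loss row beside the existing weight-gain row, with the threshold set by the sponsor (for example, mirroring the 7% gain rule). Keep the gain table.

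While editing, correct the list in SAP 10.5, where the second standing blood pressure item lacks the word diastolic.

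Cost: a few lines of SAP text and two or three descriptive tables. No new data, visits or change to conduct are needed.

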Study Days	Up to -28	0	14 + 3	28 + 3	42 + 3	56 + 3	70 + 3	84 + 3	7 Days Post Last Dose + 3	14 Days Post Last Dose + 3	30 Days Post Last Dose + 3
Study Visit Number	1	2	3	4	5	6	7	8	9	10	11
Caregiver Global Impression of Change				Х	Х	Х		Х			
Columbia Suicide Severity Rating Scale	Х	Х	Х	Х	Х	Х	Х	Х	Х	X	
Abnormal Involuntary Movement ^d		Х		Х	Х	Х		Х			
Barnes Akathisia Rating Scale		Х		X	Х	Х		Х			
Swanson, Nolan, and Pelham Questionnaire		Х		Х	Х	Х		Х			
Children's Yale-Brown Obsessive Compulsive Scale		Х		Х	Х	Х		Х			
Children's Depression Rating Scale - Revised		X		X	Х	X		Х			
Gilles de la Tourette Syndrome Quality of Life Scale		Х		X	Х	Х		Х			
Pediatric Anxiety Scale		Х		Х	Х	Х		Х			
PK Blood Draws ^{e,h}				Х				Х			
Adverse Events	Х	Х	Х	Х	Х	Х	Х	Х	Х	Х	X*
Concomitant Medications	Х	Х		Х	Х	Х		Х	Х	Х	
Dispense Study Drug		Х		Х	Х	Х		X ^f			

Assessment	Screening ^a	Baseline	Titra	tion	Т	reatmen	t	Completion/ Early Termination	7 Day Follow-up	14 Day Follow-up	30 day Follow-up*
Study Week	Up to -4	0	2*	4 ^g	6 ^g	8 ^g	10*	12 ^g	13/14 ^g	14/15 ^g	16/17
Study Days	Up to -28	0	14 + 3	28 + 3	42 + 3	56 + 3	70 + 3	84 + 3	7 Days Post Last Dose + 3	14 Days Post Last Dose + 3	30 Days Post Last Dose + 3
Study Visit Number	1	2	3	4	5	6	7	8	9	10	11
Collect Unused Study Drug/Assess drug compliance				Х	Х	Х		Х	Х		

Abbreviations: AE = adverse event; BP = blood pressure; ECG = electrocardiogram; HR = heart rate; PK = pharmacokinetic(s)

^a Informed consent must be performed prior to any screening procedures. All screening procedures are to occur after washout of any applicable medications. Rescreening is allowed after approval by the Medical Advisor.

^b Vital signs will include, pulse, BP, orthostatic BP (done 5 minutes after being supine and then 3 minutes after standing), height and weight.

^c Subjects should be in a fasting state (8 hours) for laboratory tests. HbA1c will be measured at the baseline and completion/early termination visits.

^d Every attempt should be made to perform this assessment at the same time at each visit.

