12.1.3. Other Safety Assessments

Vital signs will be collected at each clinic visit (Screening, Baseline, Weeks 4, 6, 8, 12, 7 and 14 day Follow Up visits). It includes blood pressure, orthostatic blood pressure (after being supine for 5 minutes and 3 minutes after standing) pulse, height and weight.

Clinical Laboratory Assessments:

During the following clinic visit (Screening, Baseline, Week 12, 7-day and 14 day Follow Up visits), the following clinical laboratory tests will be performed. HbA1c will be measured at the baseline and completion/early termination visits.

Clinical Laboratory Tests					
Category	Parameters				
Hematology	Red blood cell count, hemoglobin, hematocrit, platelets, and white blood cell count with differential (neutrophils, bands lymphocytes, monocytes, eosinophils, basophils)				
Chemistry					
Electrolytes	Sodium, potassium, chloride, bicarbonate				
Liver function tests	Alkaline phosphatase, aspartate aminotransferase (AST), alanine aminotransferase (ALT), total bilirubin, direct bilirubin				
Renal function parameters	Blood urea/blood urea nitrogen (BUN), creatinine				
Other	Glucose, calcium, albumin, cholesterol, triglycerides, phosphorus, lactate dehydrogenase (LDH), total protein, globulin				
Pregnancy Test	Urine test (for women of childbearing potential only)				
Special Parameters	Hemoglobin A1c (HbA1c)				

Contraception Guidelines:

As specified in the Inclusion Criteria (Section 8.1), adolescent females of childbearing potential who are sexually active and male subjects who are sexually active must use a highly effective form of contraception throughout the study and for 30 days after the last dose of study drug. See the Contraception Guidelines for additional information.

Subjects must be monitored for signs of study drug abuse, and withdrawal or dependence and if detected must be recorded as AEs.

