7.2. Demographic and Other Baseline Characteristics

Demographics and other baseline characteristics will be summarized for the Modified Intent-to-Treat Set by randomized treatment and overall. Summary statistics and by-subject listings will be provided.

Demographics and baseline characteristics will include age, sex, ethnicity, race, weight, height, body mass index (BMI).

Age at Study day 1 = (Study day 1 visit date - date of birth + 1) / 365.25 and truncated to complete years.

Height (in cm) = height (in inches) * 2.54

Weight (in kg) = weight (in lbs) * 0.4536

BMI (kg/m²) = Weight(kg)/[Height(m)²]

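### SAP 10.5 derives every BMI from the Screening height, against the protocol's height at each clinic visit, so growth in subjects aged 6 to <18 appears as within-arm BMI gain

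*SAP*

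**What the plan says.** SAP 10.5 (Vital Signs) gives two linked rules. On collection: "Body height will be measured at Screening only and will be summarized by treatment group". On derivation: "Body mass index (BMI) will be derived from the weight at each visit and from height (at screening), along with changes from baseline". SAP 7.2 defines BMI in the usual way, as weight in kilograms over height in metres squared.

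The protocol says otherwise about height. Section 12.1.3: "Vital signs will be collected at each clinic visit (Screening, Baseline, Weeks 4, 6, 8, 12, 7 and 14 day Follow Up visits". The next sentence there defines the content of vital signs: "It includes blood pressure, orthostatic blood pressure (after being supine for 5 minutes and 3 minutes after standing) pulse, height and weight". Footnote b of the schedule of assessments (Protocol Table 2) agrees: "Vital signs will include, pulse, BP, orthostatic BP (done 5 minutes after being supine and then 3 minutes after standing), height and weight". SAP 14.1 reproduces that schedule with the same footnote, so SAP 10.5 conflicts with another section of the SAP as well as with the protocol. SAP section 12 states that nothing has changed from the analysis planned in the protocol, so this is not a declared departure.

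**The concern.** Eligibility runs from 6 to under 18 years (Protocol 8.1), so many subjects will grow measurably during the study. If the height in the denominator is frozen, a child who grows in proportion, with true BMI constant, is reported as gaining BMI.

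BMI is the only planned body-size summary that could separate growth from excess weight gain. The other two in SAP 10.5, change in weight and weight gain of at least 7%, make no allowance for height. With a fixed height, the BMI-change table merely rescales the weight-change table. Because height is summarised at Screening only, growth by arm would not be shown either.

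The question is a live one for this product. Protocol 12.2.1.3 names weight gain as an adverse event of special interest. Protocol 5.3.1 reports that almost all children in the open-label extension of the earlier paediatric study gained weight. What is at stake is whether the within-arm BMI changes in the study report can be read as changes in body composition.

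**Working it through.** The documents contain no BMI-change, height or growth figure, so there is no stated number to reproduce.

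**Step 1: what the rule does algebraically.** Let w0 and w12 be the weights at Baseline and Week 12, h0 and h12 the true heights then, and hs the Screening height.

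- Reported BMI change, relative to reported Baseline BMI: (w12/hs² − w0/hs²) / (w0/hs²) = w12/w0 − 1. This is the percent weight change exactly; hs cancels.
- True BMI change: (w12/w0) × (h0/h12)² − 1.
- If true BMI is constant, w12/w0 = (h12/h0)², and the rule reports a rise of (h12/h0)² − 1.

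**Step 2: which interval applies.**

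- Change from Baseline to Week 12: both BMIs use the Screening height, so growth between Screening and Baseline cancels. The interval is 12 weeks (4 weeks of titration plus 8 of treatment, Protocol 7.1).
- BMI level at Week 12: the height may be 16 weeks old (up to 28 days of screening plus 12 weeks).
- Change from Baseline to the 14-day follow-up: the schedule places that visit at Week 14/15, so up to 15 weeks.

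**Step 3: size, under assumed growth.** Height h at the start of the interval and growth velocity v are assumptions. The artefact is ((h + v × weeks/52)/h)² − 1.

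| Assumed h, v | Change to Week 12 (12 wk) | Change to last follow-up (15 wk) | Week 12 level (16 wk) |
|---|---|---|---|
| 150 cm, 4 cm/yr | 1.2% | 1.5% | 1.6% |
| 140 cm, 6 cm/yr | 2.0% | 2.5% | 2.7% |
| 125 cm, 8 cm/yr | 3.0% | 3.7% | 4.0% |

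One cell in full: 8 × 12/52 = 1.85 cm; (126.85/125)² − 1 = 0.030.

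At the extremes, an adolescent of 165-175 cm growing 0-1 cm a year gives about 0-0.3% over 12 weeks and 0-0.4% over 16. A subject of 150 cm growing 10 cm a year gives 3.1% and 4.1%.

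**Step 4: in BMI units.** At an assumed BMI of 20, the three 12-week figures are 0.25, 0.40 and 0.60 kg/m². As a numerical check, take a Screening height of 140 cm, a Baseline weight of 35 kg and growth of 5 cm a year. Height is then 140.38 cm at Baseline and 141.53 cm at Week 12. Holding true BMI constant takes weight to 35 × (141.53/140.38)² = 35.58 kg. The SAP rule reports 0.58/1.40² = +0.29 kg/m², about 1.6%, where the true change is zero.

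**The case against.** The case for leaving this alone has several sound parts. Post-baseline BMI is a descriptive safety summary with no test, threshold or decision attached. Treatment is randomised 1:1 against placebo, so growth should be similar in the two arms and the drug-placebo difference is little affected. Weight change is reported beside BMI, and all vital-signs data are listed, so later heights could be recovered if they were recorded. SAP 4.1.1 does name the absence of dose adjustment with BMI change as an intercurrent event, but handles it by treatment policy, so the efficacy analysis does not depend on how BMI is derived. All of this stands and limits the importance of the point.

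Same-visit height also has a cost. Under footnote g of Table 2, visits from Week 4 onward may be held away from the clinic or remotely, so heights may be missing or less reliable. An assumed error of 1 cm at 140 cm moves BMI by (141/140)² − 1 = 1.4%, similar to 12 weeks of growth. Such error, if random, adds noise to individual values; growth shifts the mean in one direction.

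A reader might infer more than the documents support:

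- That reported BMI change will be inflated by 1.6-4%. Those are 16-week figures for the Week 12 level under particular growth rates. Change from Baseline to Week 12 covers 12 weeks, and adolescents near final height contribute almost nothing.
- That the 7% weight-gain tabulation is distorted. It uses body weight alone.
- That correct heights are already in the database. No case report form is among the documents. The schedule implies collection at each visit, SAP 10.5 says otherwise, and nothing settles which was done.

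**Conclusion.** The point stands as a minor inconsistency with a definite direction of bias. SAP 10.5 contradicts Protocol 12.1.3, Protocol Table 2 and SAP 14.1 on when height is measured, and SAP section 12 does not declare the difference. The identity between percent BMI change and percent weight change holds without any growth assumption. It means the BMI-change summary cannot separate growth from excess gain.

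The size rests wholly on assumed heights and velocities. For growth of 0-10 cm a year it is about 0-3% for change from Baseline to Week 12, up to about 4% for the Week 12 BMI level, and nearly 4% for change to the last follow-up. The effect is confined to descriptive within-arm BMI. The documents give no ground for extending it to the treatment comparison, the 7% tabulation or the efficacy results.

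**What to change.** Reconcile SAP 10.5 with Protocol 12.1.3, footnote b of Protocol Table 2 and SAP 14.1. State that height is measured at each clinic visit and summarised by visit and arm. Derive BMI from height and weight at the same visit; where height is missing, for example at a remote visit, use the nearest earlier height and flag the value as carried forward. The existing reference to change from baseline can stay, since SAP 6.2 already defines Baseline as the last measurement before first dose.

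If the case report form shows that height was collected only at Screening, same-visit BMI cannot be computed. In that case, record the departure in SAP section 12 and footnote the BMI tables to say that change in BMI equals change in weight in percentage terms and includes growth.

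The cost is a revision of SAP wording and one derivation, with no procedure beyond those already in the protocol schedule. The small downsides are some added noise from height measurement error and gaps where remote visits lack a height.
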